### **9.2.3. Safety**

All reported terms for AEs (ocular and systemic) will be coded using Medical Dictionary for Regulatory Activities (MedDRA®). For all AE and SAE tables, subjects will be counted once for each preferred term and each system organ class.

A TEAE will be defined as any AE with an onset date on or after the date of the first ITV injection of IP. AEs which are already present before the first ITV injection of IP and increase in severity after the first ITV injection of IP will be considered as TEAEs. Pre-existing AEs before the first ITV injection of IP with no increase in severity after the first ITV injection of IP will not be considered as TEAEs.

All TEAEs and SAEs will be summarised respectively for study eye (ocular TEAE), fellow eye (ocular TEAE) and others (systemic TEAE) by the frequency and percentage of subjects experiencing events by system organ class, preferred term and treatment group. SAEs leading to IP discontinuation and TEAEs by causality and severity will be summarised similarly. All AEs including those pre-existing before the first ITV injection of IP will be listed by subject.

In addition, systemic TEAEs will also be summarised without subjects who received Lucentis® in the fellow eye due to AMD during the study period after randomisation.

Changes in vital signs and clinical laboratory parameters will be summarised descriptively by treatment group and visit. Other safety variables will be summarised unless otherwise specified, and all safety variables will be listed.

All safety analyses will be performed using the SAF.

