Name of Sponsor/Company:	Samsung Bioepis Co., Ltd.
Name of Finished Product:	SB11 (proposed ranibizumab biosimilar)
Name of Active Ingredient:	Ranibizumab

parameter, the primary efficacy analysis will be performed for the per-protocol set (PPS-CST) with the change from baseline of CST at Week 4 using an analysis of covariance model with baseline CST as a covariate and region (or pooled centres) and treatment group as factors. The PPS-CST consists of all FAS subjects who have the first IP injection at Week 0 (Day 1) and complete procedures at Week 4 without any major protocol deviations that have impact on the CST assessment. The equivalence in CST will be declared if the two-sided 95% CI of the difference of CST LS mean changes from baseline at Week 4 between SB11 and Lucentis® lies within the pre-defined equivalence margin of <math>[-36 \mu\text{m}, 36 \mu\text{m}]</math>.
 
There is no formal adjustment of type I error rates.
 
For the primary analysis with the FAS for BCVA, missing data will be imputed for subjects who drop out for the study prior to the primary analysis time-point. A missing-at-random approach will assume that subjects who withdraw from a study had missing values similar to similar subjects who completed the study in that treatment group. This approach ensures that evidence of lack of equivalence is not diluted when there are missing data. For the components of BCVA, the missing letter will be imputed by multiple imputation method with the assumption of monotone missing pattern and regression method. For the sensitivity analyses, available case analysis and last observation carried forward analysis will be performed. All other efficacy measurements will be summarised descriptively by treatment group and visit.
 
Safety analyses
 
All reported terms for AEs (ocular or systemic) will be coded using the Medical Dictionary for Regulatory Activities (MedDRA®). AEs including ocular AEs in the study eye and/or fellow eye as well as systemic AEs will be summarised descriptively by treatment group.
 
Changes in vital signs and clinical laboratory parameters will be summarised descriptively by treatment group and visit. All other safety variables will be summarised descriptively by treatment group and visit unless specified otherwise, and all safety variables will be listed.
 
Pharmacokinetic analyses
 
Blood sampling for PK will be collected in approximately 40 subjects participating in PK evaluation (20 subjects per treatment group). Formal PK analysis will not be performed. The systemic exposure will be summarised descriptively by treatment group and visit.
 
Immunogenicity analyses
 
The number and proportion of subjects with ADA and NAb results (e.g., “positive” or “negative”) will be summarised by treatment group and visit.
 
NEI VFQ-25 analyses
	

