#### **4.3. Subject Discontinuation from Investigational Product**

The subject must be discontinued from IPs in the event of any of the following:

- Consent withdrawal by subject
  - If subjects withdraw his/her consent, Investigator must inquire the reasons for consent withdrawal as to whether it is related to the study (e.g., documented lack

of efficacy, AE or pregnancy); however, the subject could refuse to provide such reason

- If the main reason for consent withdrawal is considered related to the study, the Investigator may select appropriate reason among the reasons listed below other than consent withdrawal
- Rhegmatogenous retinal detachment or full-thickness macular hole in the study eye
- Any newly developed or aggravated ophthalmic abnormality other than AMD in the study eye which could interfere with evaluation of efficacy or safety of IP including but not limited to retinal vascular abnormality
- Any AEs in the study eye (e.g., intraocular inflammation, VA loss, increased IOP, subretinal haemorrhage, vitreous haemorrhage, local or systemic infection etc.) which in the opinion of the Investigator and/or subject would require IP discontinuation
- Intraocular surgery in the study eye (e.g., cataract operation, vitrectomy, glaucoma surgery, etc.) which in the opinion of the Investigator would require IP discontinuation
- Protocol deviations which may adversely affect the subject's safety and/or integrity of data as agreed by the Investigator and/or upon request from the Sponsor
- IP non-compliance
  - A subject misses any of first two doses (ITV injection of IP at Week 0 (Day 1) and Week 4) after randomisation
  - A subject misses two consecutive doses during the study period after randomisation
- Decision by the Investigator that the subject requires alternate treatment (e.g., other anti-VEGF agents such as bevacizumab or aflibercept, PDT, PPV etc.) to treat neovascular AMD in the study eye
- Decision by the Sponsor that IP discontinuation is in the subject's best medical interest or administrative decision for a reason (e.g., a suspicion of fraud, the subject enrolling in multiple clinical studies, lack of compliance, etc.) other than that of an AE
- Lost to follow-up
- Unmasking (except unmasking for the purpose of regulatory reporting)

- Pregnancy
- Death of any cause

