The term “severe” is often used to describe the intensity (severity) of a specific event (as in mild, moderate or severe myocardial infarction); the event itself, however, may be of relatively minor medical significance (such as severe headache). This is not the same as “serious,” which is based on subject/event outcome or action criteria usually associated with events that pose a threat to a subject’s life or functioning.

In addition, sight-threatening ocular adverse event will be reported as SAE if it meets one or more of the following criteria:

- A decrease in VA of  $\geq 30$  letters from the last assessment of VA
- A decrease in VA to the level of Light Perception or worse
- Requirement of surgical intervention (e.g., conventional surgery, vitreous tap or biopsy with ITV injection of anti-biotics, laser treatment, ITV gas injection, or retinal cryopexy) to prevent permanent loss of vision
- Severe intraocular inflammation (e.g., 4+ anterior chamber cell/flare or 4+ vitritis).
- In the investigator's opinion, medical intervention may be required to prevent permanent loss of vision.

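### The safety section ties its discontinuation summary to serious events only, so non-serious events that end treatment are counted by arm but not identified as having done so

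*Combined protocol and SAP*

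**What the plan says.** Section 9.2.3 sets out the adverse event (AE) outputs in one short paragraph.

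- **General tables.** The split by site comes first: "All TEAEs and SAEs will be summarised respectively for study eye (ocular TEAE), fellow eye (ocular TEAE) and others (systemic TEAE". Inside each of these three groups, the counts are then given "by the frequency and percentage of subjects experiencing events by system organ class, preferred term and treatment group".
- **Discontinuation, causality and severity.** "SAEs leading to IP discontinuation and TEAEs by causality and severity will be summarised similarly".
- **Listings.** "All AEs including those pre-existing before the first ITV injection of IP will be listed by subject".

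The synopsis is more general: "AEs including ocular AEs in the study eye and/or fellow eye as well as systemic AEs will be summarised descriptively by treatment group". It mentions no discontinuation table.

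The stopping rule is in section 4.3. One of its triggers begins "Any AEs in the study eye (e.g., intraocular inflammation, VA loss, increased IOP, subretinal haemorrhage, vitreous haemorrhage, local or systemic infection etc". The condition it attaches to such events is purely one of judgement: "which in the opinion of the Investigator and/or subject would require IP discontinuation". Section 4.3 also requires the reason for stopping IP to be entered in the eCRF in every case. Section 8.1.8 asks that withdrawal for an AE be kept distinct from withdrawal for personal reasons, and it says this of AEs in general.

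**The concern.** Section 9.2.3 uses two different terms in one sentence: treatment-emergent AEs (TEAEs) for causality and severity, but SAEs for discontinuation. Read literally, the discontinuation summary covers a narrower class of events than the rule that produces discontinuations.

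Evaluating the safety of both products is a secondary objective (section 2.2). How often each product had to be stopped because of an AE is a natural tolerability comparison in a biosimilar trial with up to 13 intravitreal injections (section 5.1.1). Suppose one arm had more withdrawals for low-grade intraocular inflammation or moderately raised intraocular pressure. The specified tables would show the events, mixed with events of the same kind that patients tolerated and continued through. They would not show that treatment stopped more often because of them.

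**Working it through.** There is no figure to reproduce. The check sets the provisions side by side and follows one kind of event through them.

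1. **Can a non-serious event end treatment?** Yes. The AE trigger in section 4.3 depends on whether the event is judged to require stopping. Seriousness is not a condition.

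2. **Are such events realistic under this protocol's own definitions?** Yes. Section 8.2.1 adds ocular criteria for seriousness. For inflammation the criterion is "Severe intraocular inflammation (e.g., 4+ anterior chamber cell/flare or 4+ vitritis", so a lower grade is not serious by that criterion. For visual acuity it is a loss of at least 30 letters or a fall to light perception or worse. Section 6.2.1 makes a loss of at least 15 letters reportable as an AE or SAE as appropriate, so a loss of 15 to 29 letters can be a non-serious AE. Inflammation, visual loss and raised pressure are all named in section 4.3 as examples of events that may lead to stopping. Section 8.3 treats any study-eye intraocular inflammation as an AE of special interest, whatever its grade.

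3. **Where does a non-serious TEAE that ends treatment appear?**

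| Output in the protocol | By arm? | Contains the event? | Shows that it ended treatment? |
|---|---|---|---|
| All TEAEs, by eye or systemic, organ class and preferred term (9.2.3) | Yes | Yes | No |
| TEAEs by causality and by severity (9.2.3) | Yes | Yes | No |
| SAEs leading to IP discontinuation (9.2.3) | Yes | No | Not applicable |
| By-subject AE listing (9.2.3) | No, not a summary | Yes | Not stated |
| Duration of exposure and number of injections (9.2.1) | Yes | Indirectly, through shorter exposure | No reason given |

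4. **In set terms.** Non-serious TEAEs leading to discontinuation are a subset of all TEAEs, so they are counted by arm. They do not overlap with SAEs leading to discontinuation, so they are absent from the one summary that carries the attribution.

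5. **Does another output fill the gap?** None in the supplied document. It specifies no table of TEAEs leading to discontinuation and no disposition table by reason for stopping IP. Section 9.2.3 names no separate table for AEs of special interest.

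**The case against.** The strongest reply has four parts.

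- **The events are not hidden.** A reader might infer that non-serious events ending treatment drop out of every between-arm comparison. The document does not support that. The sentence just before the one at issue summarises all TEAEs by treatment group, and causality and severity tables follow. Only the attribution to discontinuation is missing. This part stands in full and sets the limit of the point.

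- **The protocol is not the last word.** A reader might also infer that the sponsor has decided against tabulating these events. That does not follow. Section 9.2.3 does not say that other tables are excluded, and it ends with a general promise to summarise other safety variables. Section 9 defers further methods to an SAP to be finalised before the database lock for the main report, and that SAP is not in the supplied document. This stands as a caveat. It does not remove the point, because the one sentence on AEs leading to discontinuation names SAEs, and an SAP author could follow it literally. The general sentence on other safety variables is no assurance of a further discontinuation table.

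- **Discontinuation is not an endpoint.** The safety endpoints in section 6.1.2 are incidences of ocular and systemic AEs and their serious counterparts, which the planned tables cover. This stands. No listed endpoint goes unanalysed; what is lost is a useful view under the broader safety objective.

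- **Many important withdrawals will be serious anyway.** Section 8.2.1 also counts an event as serious if the investigator thinks medical intervention may be needed to prevent permanent loss of vision. This narrows the gap for sight-threatening events but does not close it for milder ones.

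The wording may simply be a slip for TEAEs. If so, the correction is easier still.

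**Conclusion.** The point holds at minor weight. As written, the discontinuation summary in section 9.2.3 is narrower than the stopping rule in section 4.3. From the specified tables one can compare, by arm, how often non-serious TEAEs occurred and how often serious events stopped treatment. One cannot compare how often AEs of any kind stopped treatment.

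The number of events affected cannot be derived. The document gives neither an expected rate of AE-related discontinuation nor the share of such events that would be non-serious, and any figure would be a guess. The conclusion does not depend on one.

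It rests on two assumptions: that SAEs in the sentence means what section 8.2.1 defines, and that the separate SAP does not already widen the table. If the SAP does, all that remains is to bring the protocol wording into line. The primary equivalence analyses, the error rates and the collection of data are unaffected.

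**What to change.** In section 9.2.3, replace the reference to SAEs leading to IP discontinuation with: *TEAEs (serious and non-serious) leading to IP discontinuation, with serious TEAEs as a subset*. Summarise these by study eye, fellow eye and systemic and by treatment group, in the same layout as the other TEAE tables. Carry the same wording into the SAP before the lock for the main report.

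The cost is one edited sentence and one extra descriptive table. The reason for stopping IP is already required in the eCRF. Confirm that the eCRF also links that reason to the individual AE. The SAE summary already planned needs such a link for serious events, and the wider table needs it for all TEAEs. No clinical rule, visit or assessment changes.

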#### **9.2.4. Pharmacokinetics**

Blood sampling for PK will be collected in approximately 40 subjects participating in PK evaluation (20 subjects per treatment group). The systemic exposure will be summarised descriptively by treatment group and visit.

If fellow eye received Lucentis® due to AMD during the study period after randomisation, the concentration measured after treatment for the fellow eye will be listed, but excluded from the summary statistics.

#### **9.2.5. Immunogenicity**

The number and proportion of subjects with ADA and NAb results (e.g., “positive” or “negative”) will be summarised by treatment group and visit.

If fellow eye received Lucentis® due to AMD during the study period after randomisation, the ADA and NAb results obtained after treatment for the fellow eye will be listed, but excluded from the summary statistics.

#### **9.2.6. NEI VFQ-25**

Subscale scores (general health, general vision, ocular pain, near activities, distance activities, vision-specific social functioning, vision-specific mental health, vision-specific role difficulties, vision-specific dependency, driving, colour vision, and peripheral vision) and the

composite score, which represent overall visual function, will be calculated, and the change from baseline will be summarised by treatment group and visit.

In addition, the subscale scores and composite score of NEI VFQ-25 will be also summarised without subjects who received Lucentis® in the fellow eye due to AMD during the study period after randomisation.

### 9.3. Determination of Sample Size

For the calculation of the equivalence margin for BCVA, the mean changes in VA were referred from two studies of Lucentis® in subjects with neovascular AMD. In MARINA study, the mean change of VA at Week 24 (SD) were -6.6 (13.31) letters and 6.5 (12.00) letters for placebo and 0.5 mg Lucentis® treatment groups, respectively. In FOCUS study, the mean change (SD) of VA at Week 24 were -5.0 (16.14) letters and 4.0 (14.41) letters for placebo and 0.5 mg Lucentis® treatment groups, respectively.

A fixed-effect meta-analysis of the above two studies estimates a weighted mean change in VA of 12.41 letters with a 95% CI [10.34 letters; 14.48 letters]. The derived equivalence limit from meta-analysis is 4.9 letters at Week 24, but by the agency recommendation the equivalence limit at Week 8 will be 3 letters for the comparison with the 90% CI of mean difference between treatment groups.

With the given equivalence margin of [-3 letters, 3 letters], 334 subjects per treatment groups was calculated with the assumptions of the mean difference of 0.5 letters and pooled standard deviation (SD) of 12.5 letters at the overall 5% significance level. Assuming a 5% loss from randomised subjects after 8 weeks, a sample size of 352 subjects per treatment groups (overall sample size of 704) will give 334 completers per treatment group after 8 weeks, which is estimated to give 80% power to detect the equivalence within the margin of 3 letters.

For the calculation of the equivalence margin for CST, the mean changes in CST were referred from two studies of Lucentis® in subjects with neovascular AMD. In MARINA study, the mean change of CST at Week 4 (SD) was 8.1 (58.1)  $\mu\text{m}$  and -106 (122.5)  $\mu\text{m}$  for placebo and 0.5 mg Lucentis® treatment groups, respectively. In PIER study, the mean change (SD) of CST at Week 4 were 15 (94.9)  $\mu\text{m}$  and -90 (140.9)  $\mu\text{m}$  for placebo and 0.5 mg Lucentis® treatment groups, respectively.

A fixed-effect meta-analysis of the above two studies estimates a weighted mean change in CST of -109.6  $\mu\text{m}$  with a 95% CI [-146.45  $\mu\text{m}$ ; -72.65  $\mu\text{m}$ ]. The derived equivalence limit from meta-analysis is 36  $\mu\text{m}$  at Week 4.

With the given equivalence margin of [-36  $\mu\text{m}$ , 36  $\mu\text{m}$ ], 290 subjects per treatment group was calculated with the assumptions of the mean difference of 0 between treatment groups, common SD of 133.3  $\mu\text{m}$  at the overall 5% significance level. Assuming a 10% loss from

FAS, a sample size of 323 per arm (overall sample size of 646) will give 80% power to detect the equivalence within the pre-defined margin.

Therefore, the sample size of 704 allows enough power to detect the equivalence between treatment groups in both situations.

## **10. DATA COLLECTION AND MANAGEMENT**

### **10.1. Data Confidentiality**

Information about study subjects will be kept confidential. Subject identification information will be labelled with a code number, and will not include the subject's name or other information that could identify them. A list linking the code and the subject's name will be kept in the Investigational site files as required by International Council for Harmonisation (ICH) Guideline for Good Clinical Practice (GCP) to protect the subject's confidentiality.

The coded information will be sent to the Sponsor (or designee) who will analyse it and report the study results both to regulatory and ethical authorities. The Sponsor may also place data on public websites or publish journal articles based upon these results. Subject names or other directly identifiable information will not appear on any reports, publications, or other disclosures of clinical study outcomes. Care will be taken to prevent subjects being identified through these publications. In addition, data may be shared with other companies or researchers to aid further research into AMD. Such data sharing practices will be covered by confidentiality agreements. No-one outside the Investigational site will have access to subject-identifiable information.

### **10.2. Monitoring**

The Sponsor has engaged the services of a CRO to perform all monitoring functions within this clinical study. The monitors will work in accordance with the CRO Standard Operation Procedures (SOPs) and have the same rights and responsibilities as monitors from the Sponsor organisation. Monitors will establish and maintain regular contact between the Investigator and the Sponsor.

Monitors will evaluate the competence of each Investigational site and inform the Sponsor about any problems relating to facilities, technical equipment or medical staff. During the study period, monitors will check that written informed consent has been obtained correctly from all subjects and that data are recorded correctly and completely. Monitors will also perform source data verification by comparing entries in the eCRF with corresponding source data and informing the Investigator of any errors or omissions. Monitors will verify adherence to the protocol at the Investigational site. All protocol deviations will be reported to the Sponsor via the Monitoring Visit Reports. Monitors will arrange for the supply of IP and ensure appropriate storage conditions are maintained.

Monitoring visits will be conducted at regular intervals according to ICH GCP. The monitor will provide written reports to the Sponsor on each occasion they make contact with the Investigator regardless of whether it is by phone or in person.

Further details on the monitoring processes and the level of source data verification to be performed will be outlined in the monitoring plan.

### **10.3. Data Handling and Record Keeping**

The Investigator must maintain essential study documents including protocol and protocol amendments, completed eCRFs, signed written ICFs and its revisions/updates, completed eCRFs, other relevant correspondence according to ICH GCP and other relevant study requirements (if applicable) until at least 2 years after the last approval of a marketing application in an ICH region and until there are no pending or contemplated marketing applications in an ICH region or at least 2 years after the formal termination of clinical development of the IP or 15 years from completion of the study, or whichever longer according to the relevant local laws and/or regulations. These documents should be retained for a longer period if required by the applicable regulatory requirements or the Investigational site, institution or private practice in which the study is being conducted. Subject identification codes (subject names and corresponding study numbers) will be retained for the same period of time. These documents may be transferred to another responsible party, deemed acceptable by the Sponsor, and who agrees to abide by the retention policies. Written notification of transfer must be submitted to the Sponsor. The Investigator must contact the Sponsor prior to disposing of any study records and obtain written permission to do so.

